4 STUDY POPULATION

4.1 Inclusion Criteria

All subjects must meet all of the following inclusion criteria:

1. 45 to 85 years of age inclusive, at randomization
2. Able and willing to provide signed informed consent to participate in this study
3. Documented diagnosis of IPF, as indicated in the American Thoracic Society (ATS)/European Respiratory Society (ERS)/Japanese Respiratory Society (JRS)/Latin American Respiratory Society (ALAT) [2011 Guidelines](#)
4. Receiving supplemental O₂ for use at rest
5. Subjects using O₂ only with exercise will not be eligible
6. Resting oxygen saturation (SpO₂) between 85 and 88% for at least 30 consecutive seconds while breathing room air (refer to [Section 5.1](#) and [Section 5.5.2](#) for details regarding confirming eligibility)

Or

Resting SpO₂ <85% for 10 consecutive seconds or, if in the opinion of the site staff, it is not safe or tolerable for the subject to continue without using their supplemental oxygen for 10 consecutive seconds whilst the SpO₂ is <85%.

Either of these 2 criteria should be met at both screening and Day 1 visits.

7. Able, in the Investigator's opinion, to walk a total of at least 100 meters at completion of the baseline 6-minute walk test (6MWT)
8. Weight \geq 40 kg
9. Able, in the Investigator's opinion, to complete the O₂ titration study unassisted at baseline (Day 1) and Days 30, 90, and 120
10. Able, in the Investigator's opinion, to comply with the study procedures, including attending the assessment visits and adhering to study requirements and restrictions.
11. Male or female of child-bearing potential willing and able to use highly effective methods of contraception from study start to 30 days after the last dose of study drug

4.2 Exclusion Criteria

Any subject who meets any one of the following criteria will be excluded from participation:

1. Forced expiratory volume in 1 second (FEV₁) / forced vital capacity (FVC) <70%
2. History of interstitial lung diseases secondary to other medical conditions (e.g., scleroderma, sarcoidosis or rheumatoid arthritis) or resulting from clinically significant environmental exposures including but not limited to, drug toxicity, hypersensitivity pneumonitis, or asbestos

3. Hospitalization due to an exacerbation of IPF within 30 days of screening
4. Documented pulmonary hypertension that is severe (World Health Organization [WHO] Functional Class IV) and/or clinically unstable, as determined by the study Investigator
 - Subjects with documented mild to moderate pulmonary hypertension on a stable regimen of therapy for at least 3 months prior to screening will be eligible for the study
5. Subject plans to begin, or has commenced, pulmonary rehabilitation within 30 days of screening
 - Subject who is on a stable exercise regimen at screening or whose regimen, in the opinion of the Investigator, is not expected to change at any time during the entire study will be considered eligible for the study
6. Corticosteroid therapy, for treatment of IPF, >10 mg per day of prednisone (or an equivalent), administered for 7 days or longer, within 30 days of screening
 - Subjects receiving a stable dose of ≤ 10 mg per day of prednisone (or an equivalent) for at least 14 days prior to screening, and in the opinion of the Investigator not anticipated to require a dose adjustment during the study, are eligible for the study
7. Corticosteroid therapy for treatment of non-IPF diseases, unless:
 - Receiving a stable dose of prednisone (or an equivalent) for at least 14 days prior to screening, and in the opinion of the Investigator not anticipated to require a dose adjustments during the study
8. Participated in another clinical trial of an investigational drug (or medical device) within 30 days or 5-half-lives, whichever is longer, prior to screening, or is currently participating in another trial of an investigational drug (or medical device)
9. Aspartate aminotransferase (AST), alanine aminotransferase (ALT) or total bilirubin $>2 \times$ upper limit of normal (ULN)
10. Serum creatinine >2.0 mg/dL
11. Clinical evidence of active infection, within 14 days of screening, which may include but is not limited to bronchitis, pneumonia, urinary tract infection, or cellulitis.
12. Active viral hepatitis within the last 6 months
13. Active tuberculosis within the last 6 months
 - Testing for latent tuberculosis is not required
14. Electrocardiogram (ECG) with a corrected QT interval using the Fridericia formula (QTcF) >450 ms (males) or QTcF >470 ms (females)
 - If ventricular pacing is noted on ECG, then QTcF intervals will not be calculated
15. Family or personal history of congenital long QT syndrome
16. Female who is breast-feeding or pregnant

17. Known current malignancy or current evaluation for a potential malignancy or history of malignancy within the past 2 years prior to screening, except for appropriately treated non-melanoma skin carcinoma, carcinoma in situ of the cervix, Stage 1 uterine cancer
18. Current smoker (including use of eCigarettes or vaporizing) or history of smoking within 3 months from screening
19. History of unstable or deteriorating cardiac or pulmonary disease (other than IPF) within 3 months of screening, including but not limited to, congestive heart failure requiring hospitalization or uncontrolled clinically significant arrhythmias
20. History of mental illness within the last 5 years, unless the subject fulfills one of the following conditions:
 - The subject has not required or been prescribed any psychiatric medication (including but not limited to antidepressants or anxiolytics) within 12 months before screening and, in the opinion of the Investigator, the subject is able and safe to participate in the study
 - The subject has been on a fixed regimen of psychiatric medications for at least 6 months before screening and displays no sign of acute mental illness and, in the opinion of the Investigator, the subject is able and safe to participate in the study
21. Other clinically significant medical disease that is uncontrolled despite treatment and is likely, in the study Investigator's opinion, to significantly impact the study's efficacy and safety assessments
22. Any condition affecting drug absorption, such as major surgery involving the stomach or small intestine (prior cholecystectomy is acceptable)
23. Known hypersensitivity to any component of the study drug

5 STUDY PROCEDURES AND EVALUATIONS

5.1 Subject Screening

The subject must be willing and able to sign and date the ICF before any screening procedures or study-specific tests may be performed.

All subjects who sign the informed consent will be given a unique study number. This number will be used to identify the subject throughout the clinical study and must be used on all study documentation related to that subject.

The screening period for a particular subject commences at the point at which the subject undergoes the first study-specific screening assessment and must be completed and evaluated within the screening period, prior to the first day of study drug dosing (Day 1). Schedules of Assessments are provided in [Appendix A \(Table 15-1 for Part A; Table 15-2 for Part B\)](#).

SpO₂ measurement for study eligibility: Assessment of resting, room air SpO₂ for study eligibility (refer to [Section 4.1, Inclusion Criteria 5](#)) is to be performed on both the screening and Day 1 visits. If the criterion is not met on either study visit day, the subject is to be screen failed without completing the other study related assessments. If the criterion is met, then the subject should proceed with the remaining assessments scheduled for that visit.

The same process is to be followed for the Day 1 visit.

Subjects may be rescreened up to 2 times, if deemed appropriate by the Principal Investigator. The rescreening visit should not occur sooner than 10 calendar days after the failed screening visit.

5.2 Avoidance of Pregnancy

Instructions for Male Subjects

There is no information about the effects GBT440 could have on the development of the fetus in humans. Therefore, it is important that the partners of male subjects do not become pregnant during the entire study and for a total 30 days after the male subject has taken the last dose of GBT440.

The methods of acceptable (highly effective) contraception that should be used by male subjects and their partners are outlined in [Section 8.6](#).

Women of Child-Bearing Potential

Pregnancy should be avoided by either absolute abstinence or the use of highly effective means of contraception (refer to [Section 8.6](#)) for the duration of the study and a total period of 30 days after the subject has taken the last dose of GBT440.

Female subjects who become pregnant during the study will have study drug discontinued but continue in the study to complete all safety follow-up assessments (refer to [Section 6.3](#)).

Women of Non Child-Bearing Potential

Female subjects are considered to be of non-child-bearing potential if they have had surgical sterilization (i.e., hysterectomy and/or bilateral oophorectomy) or if post-menopausal, having been amenorrheic for at least 2 years.

Surgical sterilization procedures should be supported with clinical documentation and noted in the relevant medical history/current medical conditions section of the eCRF.

5.3 Clinical Assessments

Screening assessments must be performed and evaluated prior to dosing on Day 1. This study has 8 visits (including the screening visit), and subjects will be enrolled for approximately 120 days from the time of first study drug dose until the last study visit. The timing of the visits, associated visit windows, and all assessments are outlined in the Schedules of Assessments provided in Appendix A ([Table 15-1](#) for Part A; [Table 15-2](#) for Part B).

5.3.1 Pregnancy

In women of childbearing potential, pregnancy testing will be performed during Screening, Day 1, Day 30, Day 60, Day 90 and Day 120 visits. During the screening visit (Day -21 to Day -1) a serum pregnancy test will be performed. Serum pregnancy test results must be available and negative prior to Day 1 dosing. During Day 1, a urine pregnancy test will be performed and the pregnancy test must be negative prior to proceeding with other study related assessments and Day 1 dosing.

5.3.2 Medical History and Demographic Data

Medical history includes currently active and past clinically significant diseases, surgeries, cancer history (including prior cancer therapies and procedures), smoking history, use of alcohol and drugs of abuse within the previous year, and IPF-associated conditions including but not limited to pulmonary hypertension, gastroesophageal reflux disease, and sleep disordered breathing.

Medical conditions that are a result of side effects (e.g., rash or diarrhea) from concomitant medications (e.g., pirfenidone or nintedanib) should be clearly defined and entered into the eCRF.

Any medical condition present at baseline should be followed during the study, and a change from the baseline status (intensity or frequency) should be reported as an AE by the Investigator (refer to [Section 10.1](#)).

All concomitant medications (e.g., prescription drugs, over-the-counter drugs, herbal/homeopathic remedies, nutritional supplements) used by the subject within 14 days prior to the screening visit should be entered on the Concomitant Medications eCRF. A start date should be entered for all medication items entered into the Concomitant Medications eCRF, including those medications used chronically.

Demographic data will include age (date of birth), sex, and self-reported race/ethnicity.

5.3.3 *Physical Examination*

A complete physical examination should include the following: an evaluation of the head, eyes, ears, nose, throat, and the cardiovascular, dermatological, musculoskeletal, respiratory, gastrointestinal, and neurological systems. A rectal or pelvic examination is not required. Any abnormality identified during screening should be recorded on the eCRF.

At subsequent visits, limited, symptom-directed physical examinations should be performed. Changes from baseline abnormalities should be recorded in the subject's study source documents. New or worsened abnormalities should be recorded as AEs on the Adverse Event eCRF.

Vital signs will include measurements of respiratory rate, heart rate, body temperature, systolic and diastolic blood pressure and oxygen saturation (SpO₂) by pulse oximetry. Blood pressure and SpO₂ measurements should be taken while the subject is in a seated or semi-recumbent position, and resting for at least 5 minutes.

5.4 Laboratory Examination

5.4.1 *Clinical Laboratory Studies*

It is the responsibility of the Investigator to assess the clinical significance of all abnormal clinical laboratory values as defined by the list of normal values on file for the local clinical laboratory. All clinically significant laboratory value abnormalities are to be recorded as AEs.

For the purpose of this study, a clinically significant laboratory value is any abnormal result that, in the judgment of the Investigator, is an unexpected or unexplained laboratory value and is accompanied by clinical symptoms and/or results in a medical intervention or corrective action (e.g., abnormalities that have clinical sequelae, require study drug dose modification, discontinuation of study drug, more frequent follow-up assessments or further diagnostic investigation). Any abnormal values that persist should be followed at the discretion of the Investigator.

Laboratory assessment time points are outlined in the Schedules of Assessments provided in Appendix A ([Table 15-1](#) for Part A; [Table 15-2](#) for Part B).

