1.5.4 Potential Risk of GBT440 Treatment

Tissue Hypoxia

There is a theoretical risk of tissue hypoxia in subjects treated with GBT440 based on the mechanism of action and the potential for impairment in O₂ offloading at the tissues. However, in vitro data show that GBT440-modified Hb remains sensitive to the Bohr effect, and in vivo data from animal models of pulmonary hypoxemia are consistent with increased oxygen extraction and consumption by tissues. Furthermore, clinical data from subjects receiving study drug and those participating in maximal cardio-pulmonary exercise tests in the ongoing Phase I/II study, GBT440-001, have not identified a concern with tissue hypoxia. Please refer to the GBT440 IB for further details.

IPF subjects in this study will be closely monitored for subclinical evidence of worsening tissue hypoxia including using assessments for erythrocytosis, increased resting heart rate and erythropoietin and laboratory tests indicating organ injury (e.g., liver aminotransferases).

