10.1 Adverse Events (AE)

An AE is defined as any untoward medical occurrence in any subject enrolled in a clinical investigation administered a pharmaceutical product, -regardless of causal attribution.

An AE can be any unfavorable and/or unintended sign, symptom, or disease temporally associated with the use of an investigational product, whether or not it is thought to be related to the investigational product. In addition to new events, any increase in the severity or frequency of a pre-existing condition that occurs is considered an AE. This includes any side effect, injury, toxicity or sensitivity reaction.

Subjects will be monitored throughout the study for AEs, from the time informed consent is obtained until the last study visit (Day 120). Reporting of AEs prior to enrollment should only include SAEs or AEs resulting from any protocol-related interventions.

AEs that are identified at the last assessment visit as specified in the protocol must be recorded in the eCRF. All events that are ongoing at this time will be recorded as ongoing on the eCRF. All (both serious and non-serious) AEs must be followed until they are resolved or stabilized, or until reasonable attempts to determine resolution of the event are exhausted. The Investigator should use his/her discretion in ordering additional tests as necessary to monitor the resolution of such events.

All reported AEs will be coded using the current version of the Medical Dictionary for Regulatory Activities (MedDRA).

All procedures specified in [Section 10.3](#) are to be followed for reporting SAEs.

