10.3.2 *Adverse Events Occurring Secondary to Other Events*

In general, AEs occurring secondary to other events (e.g., cascade of events or clinical sequelae) should be identified by their primary cause. For example, if severe diarrhea is known to have resulted in dehydration, it is sufficient to record only diarrhea as an AE or SAE on the eCRF.

However, medically significant AEs occurring secondary to an initiating event that are separated in time should be recorded as independent events on the eCRF. For example, if a severe gastrointestinal hemorrhage leads to renal failure, both events should be recorded separately on the eCRF.

10.3.3 *Persistent or Recurrent Adverse Events*

A persistent AE is one that extends continuously, without resolution between subject evaluation time points. Such events should only be recorded once in the eCRF unless the severity changes (increases or decreases). If a persistent AE becomes more or less severe, the AE should be recorded as separate AEs for each Grade of severity.

If the event becomes serious, it should be reported to the Sponsor or the Sponsor's designated CRO's Drug Safety Department within 24 hours of the Investigator, designee, or site personnel's knowledge of the event. The AE eCRF should be updated to add the SAE, providing the date that the event became serious. The updated eCRF should include both the non-serious and serious designated AEs.

A recurrent AE is one that resolves between subject evaluation time points and subsequently recurs. All recurrent AEs should be recorded separately on an Adverse Event eCRF.

10.3.4 *Abnormal Laboratory Values*

Only clinically significant laboratory abnormalities will be recorded as AEs or SAEs on the eCRF (e.g., abnormalities that require study drug dose modification, discontinuation of study drug, more frequent follow-up assessments, further diagnostic investigation).

If the clinically significant laboratory abnormality is a sign of a disease or syndrome (e.g., increased alkaline phosphatase and bilirubin associated with cholecystitis), only the diagnosis (e.g., cholecystitis) needs to be recorded on the eCRF.

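### Protocol 5.4.1 adds an expectedness condition to the AE recording of laboratory abnormalities that 10.3.4 and 10.1 lack, so values judged both expected and explained can be left out of the AE record

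*Protocol*

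**What the plan says.** Protocol 5.4.1 states that "All clinically significant laboratory value abnormalities are to be recorded as AEs". It then gives a study-specific definition: the result is one that, in the investigator's judgment, "is an unexpected or unexplained laboratory value and is accompanied by clinical symptoms and/or results in a medical intervention or corrective action". Its examples include clinical sequelae, changes to or stopping of study drug, extra follow-up and further diagnostic work.

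Protocol 10.3.4 returns to the same term: "Only clinically significant laboratory abnormalities will be recorded as AEs or SAEs on the eCRF". Its examples are "abnormalities that require study drug dose modification, discontinuation of study drug, more frequent follow-up assessments, further diagnostic investigation". It sets no condition about expectedness or explanation. It then deals with an abnormality that has a known cause, "increased alkaline phosphatase and bilirubin associated with cholecystitis", as clinically significant and to be recorded under its diagnosis.

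Protocol 10.1 is broader than either. It takes in any unfavourable or unintended finding that follows use of the drug in time, and it sets attribution aside: "whether or not it is thought to be related to the investigational product".

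The SAP covers safety only. Its endpoint (3.1) is how often TEAEs occur, how severe they are, and tolerability. Section 8.4.3 counts TEAEs, related TEAEs and TEAEs that led to stopping study drug, all from what sites recorded as AEs. Section 8.4.4 lists the clinically significant laboratory values and does not define that term.

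**The concern.** One term decides whether a laboratory abnormality becomes an AE, and the protocol describes it in two ways. The 5.4.1 description lets an explanation remove an event before it is recorded. Elsewhere the protocol takes up those questions after recording. Relatedness is judged for an AE, with pirfenidone and nintedanib toxicity taken into account (8.3). Expectedness is judged against the Investigator's Brochure (10.2.6), in support of expedited reporting (10.3.6).

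At stake are the TEAE tables and the listing of clinically significant values, both main outputs of a safety-only SAP. The study is open label, the judgment is the investigator's, and there may be up to 10 sites. Two sites could treat the same result differently and each be following the protocol.

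**Working it through.** There is no planned figure to reproduce. The check is one of logic, followed by the size of one misclassified subject.

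**Inputs.** 5.4.1 and 10.3.4 as quoted; up to about 16 subjects per part and 32 overall (Protocol 11.1, SAP 4).

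**Step 1: what 5.4.1 excludes.** The opposite of *unexpected or unexplained* is *expected and explained*. A value that is explained but unexpected, or expected but unexplained, still meets the first condition. Only values that are both fail it.

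**Step 2: compare the rules.** Take four yes/no attributes: unexpected (U), unexplained (X), symptoms (S), action (A). They give 16 combinations.

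- 5.4.1, natural reading: (U or X) and (S or A)
- 5.4.1, alternative reading in which action stands alone: ((U or X) and S) or A
- 10.3.4, taking its examples as sufficient: A

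| Value | S | A | 5.4.1 natural | 5.4.1 alternative | 10.3.4 by its examples |
|---|---|---|---|---|---|
| Expected and explained (1 of 4 U/X pairs) | no | no | no | no | no |
| | no | yes | **no** | yes | **yes** |
| | yes | no | no | no | not named |
| | yes | yes | **no** | yes | **yes** |
| Any other (3 of 4 U/X pairs) | no | no | no | no | no |
| | no | yes | yes | yes | yes |
| | yes | no | yes | yes | not named |
| | yes | yes | yes | yes | yes |

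On the natural reading, 10.3.4 includes and 5.4.1 excludes 2 of the 16 combinations. Both are expected and explained values that lead to action. On the alternative reading no such combination remains. In 3 further combinations (symptoms without action, not both expected and explained) 5.4.1 includes the value and the 10.3.4 examples do not name it. Since those are only examples, this is a gap in wording rather than an exclusion.

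**Step 3: which actions are affected.** Protocol 8.3, 8.3.1 and 8.3.2 tie modification, adjustment and interruption of study drug to an AE. In 6.3, the listed stopping reason that would cover a laboratory toxicity is also an AE. A site acting on study drug under these sections has in effect already called the finding an AE. What mainly remains is extra follow-up, further investigation, a change in background drug (8.3.3), or symptoms.

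**Step 4: what is lost and what is kept.** Lost: the AE record, the SAP 8.4.3 tables and the SAP 8.4.4 listing of clinically significant values. Kept: summaries of values and changes for laboratory parameters including erythropoietin (SAP 8.4.4), the subject listings (SAP 8.1; Protocol 11.3.2 adds high/low flags), and all discontinuations, reductions and interruptions with reason AE or Other (SAP 8.4.1).

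**Step 5: size per subject.** 1/16 = 6.25 points in a dose group; 1/32 = 3.1 points overall. This applies to the specific preferred term. Subjects are counted once, so overall TEAE incidence moves only if the subject has no other TEAE.

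**The case against.** The strongest reply is that 5.4.1 is the definition and 10.3.4 a shorter restatement. The examples in 10.3.4 nearly repeat those in 5.4.1, and 5.4.1 already names stopping study drug as an example of significance. The sentence can also be read so that action alone suffices, and then the conflict over action disappears. Part of this stands: the fault is one term described inconsistently, not two opposing rules. It does not dispose of the point. The repeated verb and the position of *and/or* favour the two-condition reading, the cholecystitis example does not fit that reading comfortably, and a recording rule that bears two readings needs correcting anyway.

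A reader might infer more than the documents support:

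- *Toxicity that stops study drug goes uncounted.* The study-drug rules largely presuppose an AE, and every discontinuation still appears in the SAP 8.4.1 exposure table, if only under Other.
- *The changes the sponsor foresees are the ones excluded.* Section 1.5.4 says subjects will be monitored "using assessments for erythrocytosis, increased resting heart rate and erythropoietin and laboratory tests indicating organ injury", but it calls tissue hypoxia a theoretical risk and says clinical data have raised no concern. Monitoring for a change does not make it expected, and an investigator could properly judge such a rise unexpected.
- *Any aminotransferase rise put down to pirfenidone or nintedanib is excluded.* Being explained is not enough; it must also be expected. The documents permit these drugs and ask that their toxicity be considered, but do not say that they raise aminotransferases.
- *TEAE rates will shift by a stated amount.* The documents give no number of affected subjects, so only the step per subject can be given.

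**Conclusion.** The point holds in a limited form. On its natural reading, 5.4.1 keeps out of the AE record a laboratory abnormality judged both expected and explained, even when it has symptoms or leads to action. Sections 10.3.4 and 10.1 contain no such condition. The practical gap is mostly follow-up, investigation and background-drug changes. It affects the TEAE tables and the clinically significant listing, not the laboratory summaries or the exposure table.

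The step is 6.25 points per subject in a part, or 3.1 points overall, for the specific term. It would be larger if fewer than 16 or 32 subjects are dosed. The conclusion rests on the two-condition reading of 5.4.1 and on sites following that section as written. The total effect cannot be estimated from the documents. This is a wording fault with a modest likely effect, worth correcting because it decides what enters the safety endpoint.

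**What to change.** In 5.4.1, delete the first condition of the definition, up to and including the first *and*, so that it begins at *is accompanied by*. Keep the existing examples. Add that presumed cause and expectedness play no part in whether the abnormality is recorded. Then have 10.3.4 and the listing in SAP 8.4.4 refer to that definition.

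The single definition should sit in 5.4.1, because 10.3.4 does not mention symptoms and cannot serve unchanged. The 10.3.4 instruction to record a diagnosis in place of its laboratory signs can stay. Under the amended text, all three expected-and-explained combinations with symptoms or action qualify.

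The cost is one sentence in the protocol, two cross-references, a matching line in any site instructions for the AE form, and slightly more AEs recorded. No clinical management rule changes.
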